1 PROTOCOL SYNOPSIS

Trial Sponsor	Alcon Research, Ltd.
	[name]
Name of Test Product	DD T2
Name of Control	ACUVUE OASYS® Brand Contact Lenses 1-Day with
Products	HydraLuxe™ Technology (Oasys 1-Day)
	CooperVision® MyDay® (MyDay)
	• 1-Day ACUVUE® MOIST (Moist)
Title of Trial	Clinical Comparison of 4 Daily Disposable Soft Contact Lenses
Protocol Number	CLE383-C004
Number of Sites	~3
Country	US
Planned Duration of	~20 days total duration
Exposure	• Test Product: 8 days (-1/+2 days)
1 -	 Control Products: 8 days (-1/+2 days)
Number of Subjects	Target to complete: 60 (20 per each parallel group)
	Planned to enroll: ~66 (~22 per each parallel group)
Study Population	Volunteer subjects aged 18 or over who are soft daily disposable
	contact lens wearers (excluding current Oasys 1-Day, MyDay, and
	Moist wearers), have at least 3 months of contact lens wearing
	experience, and who wear their habitual lenses at least 5 days per week
	and at least 8 hours per day.
Objectives	The primary objective of this study is to evaluate the overall
-	performance of DD T2 lenses when compared to Oasys 1-Day, MyDay,
	and Moist lenses.
Endpoints	Primary Effectiveness
_	Overall quality of vision

Document: TDOC-0054506 Version: 1.0; CURRENT; Most-Recent; Effective

Status: Effective Page 3 of 38

	Safety		
	• AEs		
	Biomicroscopy findings		
	Device deficient		
Assessments	Effectiveness		
Assessments	- VA (Snellen distance)		
	- VA (Shehen distance)		
	Occupation of civic		
	- Overall quality of vision	n	
	Safety		
	- AEs		
	- Biomicroscopy		
	- Device deficiencies		
Study Design	□ Prospective	Single-masked	
study Design	Single group	(trial subject)	
	Parallel group	Single-masked (Investigator)	
	Crossover	Double-masked	
	Other	Open-label	
		Other	
	Contralateral	Randomized	
	Bilateral	Kandonnized	
	Monocular lens wear		
		over group study design. In each arm, the	
		pared to one of 3 chosen control lenses.	
		l be randomized to 1 of the 6 lens	
		sover sequences of test vs. control within	
		Subjects will wear the assigned study	
		nately 1 week before crossing over into	
	the assigned study Lens 2 bilat same design will be scheduled	erally for approximately 1 week. This for each of the 3 arms.	

Document: TDOC-0054506 Version: 1.0; CURRENT; Most-Recent; Effective

Status: Effective Page 4 of 38

	Study Visits:			
	1. Baseline/Dispense Lens 1			
	2. Day 8 (-1/+2 days) follow-up Lens 1/Dispense Lens 2			
	3. Day 8 (-1/+2 days) follow-up Lens 2/Exit			
Test Product Details	Primary component/material			
	Product Name	DD T2		
	LID Number	LID 006841		
	Manufacturer	Alcon		
	Other	The lenses will be available in		
		-1.00 D to -6.00 D (0.25 D steps)		
Control Product 1	Primary component/material	senofilcon A		
Details	Product Name	Oasys 1-Day		
	LID Number	LID 009601		
	Manufacturer	Johnson and Johnson Vision		
	Other	The lenses will be available in		
		-1.00 D to -6.00 D (0.25D steps)		
Control Product 2	Primary component/material	stenfilcon A		
Details	Product Name	MyDay		
	LID Number	LID 009602		
	Manufacturer	CooperVision		
	Other	The lenses will be available in		
		-1.00 D to -6.00 D (0.25 D steps)		
Control Product 3	Primary component/material	etafilcon A		
Details	Product Name	Moist		
	LID Number	LID 009603		
	Manufacturer	Johnson and Johnson Vision		
	Other	The lenses will be available in		
		-1.00 D to -6.00 D (0.25 D steps)		
Inclusion Criteria	1. Subject must be at least 18	years of age.		
	2. Subject must be able to und	derstand and must sign an ICF that has		
	been approved by an IRB.			
	3. Successful wear of daily di	sposable spherical soft contact lenses in		
	both eyes for a minimum o	f 5 days per week and 8 hours per day		
	during the past 3 months.			
	4. Manifest cylinder ≤ 0.75 D	 		
	5. BCVA 20/25 or better in each eye.			
		stop wearing their habitual contact		
	lenses for the duration of study participation.			
Exclusion Criteria	1. Any anterior segment infection, inflammation, or abnormality or			
	disease (including systemic) that contraindicates contact lens wear,			
	as determined by the Inves	_		
	1	2. Any use of systemic or ocular medications for which contact lens		
		ted, as determined by the Investigator.		
		ry or plan to have refractive surgery		
	during the study or irregular cornea in either eye.			

Document: TDOC-0054506 Version: 1.0; CURRENT; Most-Recent; Effective

Status: Effective Page 5 of 38

Status: Effective	1 agc 3 01 36
	4. Ocular or intraocular surgery (excluding placement of punctal plugs) within the previous 12 months or planned during the study.
	5. Biomicroscopy findings at screening that are moderate (Grade 3) or
	higher and/or corneal vascularization that is mild (Grade 2) or higher.
	6. Current or history of pathologically dry eye in either eye that, in the
	opinion of the Investigator, would preclude contact lens wear.
	7. Current or history of herpetic keratitis in either eye.
	8. Eye injury in either eye within 12 weeks immediately prior to enrollment for this trial.
	9. Current or history of intolerance, hypersensitivity, or allergy to any
	component of the study products.
	10. Wearing habitual contact lenses in an extended wear modality
	(routinely sleeping in lenses for at least 1 night per week) over the
	last 3 months prior to enrollment.
	11. Any use of topical ocular medications and artificial tear or
	rewetting drops that would require instillation during contact lens wear.
	12. The Investigator, his/her staff, family members of the Investigator,
	family members of the Investigator's staff, or individuals living in
	the households of the aforementioned persons may not participate in the study.
	13. Participation of the subject in a clinical trial within the previous 30
	days or currently enrolled in any clinical trial.
	14. Currently wearing Oasys 1-Day, MyDay, or Moist contact lenses.
	15. Habitually wearing monovision or multifocal lenses during the last
	3 months.
Associated Materials	Lubrication/re-wetting drops will not be permitted.

Table 1-1 Schedule of Study Procedures and Assessments

Procedure/ Assessment	Visit 1, Day 1: Baseline/ Dispense Lens 1	Visit 2, Week 1: Day 8 of lens wear (-1/+2 days) Follow-up Lens 1/ Dispense Lens 2	Visit 3, Week 2: Day 8 of lens wear (-1/+2 days) Follow-up Lens 2/ Exit	Unscheduled Visit
Informed Consent	nformed Consent ✓ -		-	-
Demographics	✓	-	-	-
Medical History	✓	-	-	-
Concomitant Medications	✓	(✓)	(✓)	(✓)
Inclusion/ Exclusion ✓		-		-
Habitual lens (brand, power)*	✓	-	-	-

Document: TDOC-0054506

 $\begin{tabular}{ll} \textbf{Version:} & 1.0; & \texttt{CURRENT}; & \texttt{Most-Recent}; & \texttt{Effective} \\ \end{tabular}$

Status: Effective				Page 6 of 38
Procedure/ Assessment	Visit 1, Day 1: Baseline/ Dispense Lens 1	Visit 2, Week 1: Day 8 of lens wear (-1/+2 days) Follow-up Lens 1/ Dispense Lens 2	Visit 3, Week 2: Day 8 of lens wear (-1/+2 days) Follow-up Lens 2/ Exit	Unscheduled Visit
VA w/ habitual correction (OD, OS, Snellen distance)*	✓	-	✓	(✓)
Biomicroscopy	✓	✓	✓	✓
Dispense study lenses	✓	✓	-	-
VA w/ study lenses (OD, OS, Snellen distance)	✓	✓	✓	(✔)
Subjective rating with study lenses: output output	-	✓ (Follow-up Lens 1)	✓	✓

Document: TDOC-0054506 Version: 1.0; CURRENT; Most-Recent; Effective

Status: Effective Page 7 of 38

Procedure/ Assessment	Visit 1, Day 1: Baseline/ Dispense Lens 1	Visit 2, Week 1: Day 8 of lens wear (-1/+2 days) Follow-up Lens 1/ Dispense Lens 2	Visit 3, Week 2: Day 8 of lens wear (-1/+2 days) Follow-up Lens 2/ Exit	Unscheduled Visit
AEs	✓	✓	✓	✓
Device deficiencies	✓	✓	✓	✓
Exit Form	(✓)	(<)	(✓)	(✓)

^(✓) assessment performed as necessary, eg, decrease of VA by 2 lines or more with investigational product (IP)

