3.4 Subject Population

The study population includes approximately 66 volunteer subjects to be enrolled at approximately 3 sites, with approximately 22 subjects enrolled per site. The study population will consist of subjects with normal eyes (other than the need for optical correction for myopia), and who are adapted, existing wearers of daily disposable soft contact lenses in both eyes.

Subjects must be screened according to the full list of inclusion/exclusion criteria in Section 1 of this protocol. Rescreening of subjects is not allowed in this study.

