5 STUDY PROCEDURES AND ASSESSMENTS

5.1 Visits and Examinations

5.1.1 Visit 1 (Day 1) – Baseline/Dispense Lens 1

1	Explain the purpose and nature of the study, and have the subject read, sign, and date
	the IRB-approved informed consent document. Additionally, have the individual
	obtaining consent from the subject and a witness, if applicable, sign and date the
	informed consent document. Provide a photocopy of the signed document to the
	subject and place the original signed document in the subject's chart. After signing
	the ICF, a subject will be assigned a subject number by the EDC system. A signed
	informed consent document defines the point of enrollment.
2	Obtain demographic information and medical history, including information on all
	medications used within the past 30 days. Include herbal therapies, vitamins, and all
	over-the-counter as well as prescription medications.
3	
4	Perform Snellen VA with habitual correction.
	OD, OS, distance only, contact lenses
	Over-refraction (only needed if VA is reduced)
	Record habitual lens information (brand, power).
5	
6	

[figure not shown]
Document: TDOC-0054506 Version: 1.0; CURRENT; Most-Recent; Effective

Status: Effective Page 16 of 38

7	Perform slit-lamp biomicroscopy (without contact lenses) to evaluate the following:	
	Limbal hyperemia	
	Bulbar hyperemia	
	Corneal staining	
	Conjunctival staining	
	Palpebral conjunctival observations	
	Corneal epithelial edema	
	Corneal stromal edema	
	Corneal vascularization	
	Conjunctival compression/indention	
	• Chemosis	
	Corneal infiltrates	
	Other findings	
8		
9	Review inclusion/exclusion criteria to determine if the subject qualifies to be	
	randomized into the study. If subject qualifies, request randomization. If subject does	
	not qualify, exit the subject from the study as a screen failure.	
10	Based upon the randomized treatment sequence assignment, have the subject insert	
	the appropriate study lenses.	
	Keep all lidding foils of lenses used during lens fit process for study lens	
	accountability.	
11	Follow procedures to maintain masking.	
11		
12	Evaluate the study lenses by performing the following:	
12	Snellen VA with study lenses (OD and OS, at distance)*	
	Over-refraction if necessary to determine the best contact lens-corrected VA	
	and final study lens power(s)	
	*VA w/study lenses must be 20/40 OU or better for subject to leave the office	

Document: TDOC-0054506 Version: 1.0; CURRENT; Most-Recent; Effective

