5.3 Discontinued Subjects

Discontinued subjects are those who withdraw or are withdrawn from the study after signing the informed consent, including screen failures. Subjects may discontinue from the study at any time for any reason. Subjects may also be discontinued from the study at any time if, in the opinion of the Investigator, their continued participation poses a risk to their health. Discontinued subjects will not be replaced (ie, their subject numbers will not be re-assigned/re-used).

Should a subject exhibit any clinically relevant signs, symptoms, or other clinical observations that possibly could be associated with suspected sensitivity or intolerance to one of the study treatments, the Investigator must document those observations on an AE Form.

Any subject who exits early from the study (excluding screen failures) must undergo all procedures outlined at Visit 3, as applicable.

Document: TDOC-0054506 Version: 1.0; CURRENT; Most-Recent; Effective

Status: Effective Page 22 of 38

The Investigator must document the reason for study or treatment discontinuation in the subject's case history source documents.

To ensure the safety of all subjects who discontinue early, Investigators must assess each subject and, if necessary, advise them of any therapies and/or medical procedures that may be needed to maintain their health.

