1.3 Randomization

A member of the Randomization Programming group at Alcon who is not part of the study team will generate the randomized allocation schedule(s) for study lens sequence assignment. Randomization will be implemented in iMedidata Balance.

Qualifying subjects will be randomized in a 1:1:1:1:1 manner to one of 6 lens sequences consisting of the test lens and a control lens as described below. For each sequence, subjects wear 1st lens then crossover to 2nd lens.

Sequence 1: DD T2/Oasys 1-Day

Sequence 2: Oasys 1-Day/DD T2

Sequence 3: DD T2/MyDay

Sequence 4: MyDay/DD T2

Sequence 5: DD T2/Moist Sequence 6: Moist/DD T2

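### Does counting enrolment from consent leave the planned 66 subjects short of the 60 completers?

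*Protocol*

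**What the plan says.** The Protocol synopsis, repeated in SAP Table 1-1, states two numbers: "Target to complete: 60 (20 per each parallel group") and "Planned to enroll: ~66 (~22 per each parallel group"). Section 3.4 restates the second by site: "approximately 66 volunteer subjects to be enrolled at approximately 3 sites, with approximately 22 subjects enrolled per site".

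Section 5.1.1, step 1, says that the signed "informed consent document defines the point of enrollment". Eligibility is reviewed at step 9 of the same visit. Subjects who qualify are then randomised, and the others leave as screen failures. The note at step 8 of Section 5.1.3 likewise treats enrolled subjects as either screen failures or randomised.

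Section 5.3 states: "Discontinued subjects are those who withdraw or are withdrawn from the study after signing the informed consent, including screen failures". It adds: "Discontinued subjects will not be replaced", and a parenthesis explains that their subject numbers will not be used again.

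SAP Section 1.3 reads: "Qualifying subjects will be randomized in a 1:1:1:1:1 manner to one of 6 lens sequences". It then lists all six sequences.

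**The concern.** The protocol defines enrolment at consent, counts screen failures among discontinued subjects, and says that discontinued subjects are not replaced. Taken together, these statements suggest that the step from 66 to 60 must absorb every loss after consent, including losses at screening. Screening losses are plausible: eligibility depends partly on findings at Visit 1 (cylinder, best corrected acuity, biomicroscopy grades), and wearers of three marketed lenses are excluded.

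If sites stopped at 66 consents, the trial could finish below 20 completers per group. That target is the only sample-size commitment in the visible text. The five-term ratio for six sequences adds to the impression that the counts were not checked against the design.

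**Working it through.** **Inputs.** Completers 60 (20 per group) and planned enrolment about 66 (about 22 per group), from the Protocol synopsis and SAP Table 1-1. Six sequences, from Protocol Section 4 and SAP Section 1.3. The visible text gives no screen-failure rate *s* and no dropout rate *d* after randomisation, so both are assumptions below.

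**1. The plan's own figure.** The implied loss is 1 − 60/66 = 1 − 20/22 = 9.1%. Inflating for dropout alone, N/(1 − d), with d = 9.1% gives 60/0.909 = 66 and 20/0.909 = 22. The simpler 60 × 1.10 also gives 66. So 66 is reproduced as an allowance of about 9–10% for dropout, with nothing added for screening. Over six sequences, 66/6 = 11 each.

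**2. The literal reading, with 66 as consents.** Expected completers are 66(1 − s)(1 − d), and the number completing is Binomial(66, (1 − s)(1 − d)).

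| s | d | Expected completers | Per group | P(at least 60) |
|---|---|---|---|---|
| 0 | 5% | 62.7 | 20.9 | 0.95 |
| 5% | 2% | 61.4 | 20.5 | 0.83 |
| 5% | 5% | 59.6 | 19.9 | 0.53 |
| 10% | 5% | 56.4 | 18.8 | 0.14 |
| 15% | 5% | 53.3 | 17.8 | 0.02 |

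**3. How much screening loss the literal reading tolerates.** The largest s that still gives 60 in expectation is 1 − (60/66)/(1 − d). This is 9.1% at d = 0, 7.2% at d = 2%, 4.3% at d = 5% and 0 at d = 9.1%. Screening loss has to be almost nil only if dropout alone uses most of the allowance.

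**4. Which reading the text supports.** A parallel group exists only after randomisation, and a screen failure never receives a sequence. About 22 per group therefore cannot count consents. With 66 randomised, expected completers are 66(1 − d), which is at least 60 for any d up to 9.1%. The number of consents needed to randomise 66 is 66/(1 − s): 70 at s = 5%, 74 at 10%, 78 at 15%.

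**5. Whether anything stops sites from consenting that many.** The synopsis, Section 3.4 and SAP Table 1-1 all give approximate figures, and Section 3.4 contains no instruction to stop at 22. Section 5.3 explains non-replacement as not re-using subject numbers, which does not bar further subjects.

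**6. Balance across sequences.** Screen failures exit at step 9 of Visit 1, before allocation. They reduce the number randomised but do not by themselves unbalance the sequences.

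**7. Effect on the results.** Effectiveness is summarised on the Safety Analysis Set, which contains subjects exposed to study lenses (Protocol Sections 6.2.1 and 6.4). Screen failures are not exposed and so do not enter it. Standard errors scale with 1/√n. At 18.8 instead of 20 per group the factor is √(20/18.8) = 1.03. At 17.8 it is √(20/17.8) = 1.06.

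**The case for a change.** The strongest opposing case is that the protocol defines enrolment explicitly, confirms the definition in Section 5.1.3, and then uses the same word for a number that fits only randomised subjects. A site reading the definition strictly could count consents towards its 22. Nothing visible says that screen failures fall outside the 66 or that extra subjects may be enrolled. With no power calculation in view, the completer target is the one number against which recruitment can be judged.

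The mismatch in terms stands, and so does the arithmetic on the literal reading. The shortfall does not. It needs a hard cap that the text does not set, together with loss rates that the documents do not give. Sections of both documents are blacked out (an entry after Section 6.9 in the Protocol contents, and SAP Section 7), so the absence of a sample-size statement from the visible text is no evidence that none was written.

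The five-term ratio is an error on the page, but the same sentence says six sequences and the list beneath it names all six. Equal allocation is the only sensible reading.

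**Conclusion.** The concern does not call for a change. The figure of 66 is a count of randomised subjects described with the word enrol, and on that reading the plan's arithmetic is correct: a 9.1% dropout allowance yields 60 completers. The five-term ratio is a clerical slip that the accompanying list resolves.

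An expected shortfall arises only if 66 is treated as a ceiling on consents and screening losses exceed about 4% at 5% dropout, or about 9% at no dropout. These thresholds depend on assumed rates. Even at 10% and 5%, the cost is about 1.2 completers per group and a 3% wider standard error.

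No test, margin or decision depends on reaching 60. Protocol Section 6.4.1.1 and SAP Section 4.2 state no hypotheses, and the SAP executive summary says that success criteria do not apply. Replacing one verb would alter no analysis, and restating the completer target at about 56 would put assumed loss rates in place of the stated goal.

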1.1 Abbreviations

Table 1–2 Table of Abbreviations

Abbreviation	Definition
ADE	Adverse device effect
ASADE	Anticipated serious adverse device effect
AE	Adverse event
BCVA	Best corrected visual acuity
CFR	Code of Federal Regulations
D	Diopter
DD	Daily Disposable
eCRF	Electronic case report form
EDC	Electronic data capture
FDA	US Food and Drug Administration
GCP	Good Clinical Practice
IB	Investigator's brochure
ICF	Informed consent form
IP	Investigational product
IRB	Institutional review board
ISO	International Organization for Standardization
mm	Millimeter
MOP	Manual of procedures
N/A	Not applicable
OD	Right eye
OS	Left eye
OU	Both eyes
SAE	Serious adverse event
SADE	Serious adverse device effect
US	United States
USADE	Unanticipated serious adverse device effect
VA	Visual acuity

^{*} Source only

[†] Comments, optional

Status: Effective Page 8 of 38

3 INTRODUCTION

3.1 Study Rationale and Purpose

The purpose of this study is to obtain on-eye performance data to inform contact lens product development and to further evaluate product performance in the intended population. The primary endpoint was selected to fulfil the primary objective of the study. Procedures for measurement of these endpoints were selected based on common practice for these assessments. The design of this study is justified based upon preclinical and clinical testing, as described within the Investigator's Brochure. Oasys 1-Day, MyDay, and Moist contact lenses were chosen as the control products because these lenses have the same wear modality. The new contact lens in development is intended for the optical correction of refractive myopia in persons with non-diseased eyes.

There are no immediate plans to submit the results of this study for publication; however, the results may be offered for publication if they are of scientific interest, or if the results relate to a product that is subsequently approved or cleared for marketing.

3.2 Trial Objective

The primary objective of this study is to evaluate the overall performance of DD T2 lenses when compared to Oasys1-Day, MyDay, and Moist lenses.

3.3 Risks and Benefits

Contact lenses may offer improved peripheral vision and the convenience of not wearing spectacles. Material properties and design characteristics of the contact lens in development are features consistent with successful contact lens wear.

Based upon non-clinical testing and/or documented rationale for applicability of test results to the IP, the new contact lens in development is assessed to be non-toxic and biocompatible for on-eye use.

The new contact lens in development and the 3 control contact lenses are not intended for use with a cleaning/disinfecting solution, and the biocompatibility with lens care solutions and any associated clinical effects are unknown.

A summary of the known potential risks and benefits associated with the new contact lens in development can be found in the Investigator's Brochure. There may also be unknown risks with the use of the new contact lens. Risks are minimized by compliance with the eligibility criteria and study procedures, and through close supervision by a licensed clinician during

Document: TDOC-0054506 Version: 1.0; CURRENT; Most-Recent; Effective

Status: Effective Page 12 of 38

exposure to the study lenses. The potential harms associated with on-eye exposure to the new lens materials include toxicity response, blurred vision and ocular discomfort. In general, the risks with the new contact lens in development are anticipated to be similar to other marketed daily disposable soft contact lenses.

The site personnel will educate subjects on proper hygiene and lens handling, and compliance with the use of contact lenses according to the protocol. Subjects should be instructed not to wear contact lenses while sleeping or swimming. The site personnel will also advise the subjects to remove contact lenses and return for prompt follow-up of symptoms, such as ocular discomfort, foreign body sensation, excessive tearing, vision changes, or hyperemia.

3.4 Subject Population

The study population includes approximately 66 volunteer subjects to be enrolled at approximately 3 sites, with approximately 22 subjects enrolled per site. The study population will consist of subjects with normal eyes (other than the need for optical correction for myopia), and who are adapted, existing wearers of daily disposable soft contact lenses in both eyes.

Subjects must be screened according to the full list of inclusion/exclusion criteria in Section 1 of this protocol. Rescreening of subjects is not allowed in this study.

